### **Serious Adverse Event (SAE):**

An SAE is defined as any untoward medical occurrence that:

- results in death,
- is life-threatening (Note: the term “life-threatening” refers to an event in which the subject was at risk of death at the time of the event rather than to an event which hypothetically might have caused death if it were more severe.),
- requires in-patient hospitalization or prolongation of existing hospitalization,
- results in persistent or significant disability/incapacity, or
- is a congenital anomaly/birth defect.

Medical and scientific judgment should be exercised in deciding whether expedited reporting is appropriate in other situations, such as important medical events that may not be immediately life-threatening or result in death or hospitalization but may jeopardize the subject or may require intervention to prevent one of the other outcomes listed in the above definition. These events should be considered serious.

#### **9.1.1. Assessment of Severity**

The Investigator will assess the intensity of the AE and rate the AE as mild, moderate, or severe using the following criteria:

**Grade 1 – Mild:** These events are easily tolerated, require minimal or no treatment, and do not interfere with the subject’s daily activities.

**Grade 2 – Moderate:** These events cause sufficient discomfort to interfere with daily activity and/or require a simple dose of medication, e.g., analgesics or anti-emetics.

**Grade 3 – Severe:** These events incapacitate and prevent usual activity or require complex medication/treatment or hospitalization.

**Grade 4 – Life Threatening:** These events are those for which the subject was at risk of death at the time of the event rather than an event which hypothetically might have caused death if it were more severe.

**Grade 5 – Death:** The event resulted in the death of the subject.

Changes in the severity of an AE should be documented to allow for an assessment of the duration of the event at each level of intensity to be performed.

#### **9.1.2. Assessment of Causality**

The Investigator will assess the relationship or association of the investigational product in causing or contributing to the AE, which will be characterized using the following classification and criteria:

**Definite:** AEs that, after careful medical evaluation, are considered definitely related to the investigational product; other conditions (concurrent illness, progression/expression of disease state, or concurrent medication reaction) do not appear to explain the event.

**Probable:** AEs that, after careful medical evaluation, are considered with a high degree of certainty to be related to the investigational product. The following characteristics will apply:

- a reasonable temporal relationship exists between the event and exposure to the investigational product, and
- the event is a known reaction to the investigational product that cannot be explained by an alternative cause commonly occurring in the population/individual, or
- the event is not a known reaction to the investigational product but cannot be reasonably explained by an alternative cause.

**Possible:** AEs that, after careful medical evaluation, do not meet the criteria for a definite or probable relationship to the investigational product, but for which a connection cannot be ruled out with certainty. The following characteristics will apply:

- the event occurs after exposure to the investigational product, and
- there is a reasonable temporal relationship to the application, but the event is not a known reaction to the investigational product and could be explained by a commonly occurring alternative cause, or
- in the absence of a reasonable temporal relationship, the event cannot be explained by an alternative cause.

**Not related:** AEs in this category will have either of the following characteristics:

- the event does not have a reasonable temporal relationship to investigational product administration and/or can be explained by a commonly occurring alternative cause.

### **9.1.3. Follow up of Adverse Events**

The Investigator will follow a non-serious AE until resolution, stabilization, or the End of Study Visit. The Investigator will follow an SAE (regardless of relationship to investigational product) until the event resolves, stabilizes, or becomes non-serious. All AEs identified on the last scheduled contact must be recorded on the AE page of the eCRF and current status (ongoing or resolved) will be noted. In addition, SAEs will be reported to Worldwide Clinical Trials Drug Safety ([[contact]](mailto:[contact])) according to the reporting guidelines identified in [Section 9.2.2](#).

## **9.2. Monitoring of Adverse Events**

### **9.2.1. All Adverse Events**

All AEs will be analyzed for safety. Those meeting the definition of SAE must be reported using the SAE Form. Subjects should voluntarily report any AEs or report AEs in response to general, non-directed questioning (e.g., "How has your health been since the last visit?"). For each AE volunteered by the subject, the Investigator should obtain all the information required to complete the AE page of the eCRF, in accordance with the guidelines that accompany it.

All AEs, regardless of seriousness, severity, or presumed relationship to investigational product, must be recorded using medical terminology in the source document and on the eCRF.

Whenever possible, diagnoses should be given when signs and symptoms are due to a common etiology (e.g., cough, runny nose, sneezing, sore throat, and head congestion should be reported as "upper respiratory infection"). Investigators must record on the eCRF their opinion concerning the relationship of the AE to investigational therapy. All measures required for AE management must be recorded in the source document and reported according to Sponsor instructions.

Any non-serious AE that occurs after administration of investigational product must be reported in detail on the appropriate eCRF page and followed until resolution, stabilization, or the End of Study Visit. The description of the AE will include description of event, date of onset, date of resolution, Investigator assessment of severity and relationship to investigational product (with rationale), seriousness (with rationale), any required treatment or evaluations, and outcome.

The Sponsor assumes responsibility for appropriate reporting of AEs to the regulatory authorities. The Sponsor will also report to the Investigators all SAEs that are unlisted in the Investigator's Brochure and associated with the use of the investigational product. The Investigators must report these events to the appropriate Institutional Review Board (IRB) in accordance with local regulations.

### **9.2.2. Serious Adverse Events**

All SAEs occurring during clinical studies must be reported within 24 hours to Worldwide Clinical Trials Drug Safety.

The cause of death of a subject in a clinical study, whether the event is expected or associated with the investigational product, is an SAE.

The initial report of an SAE may be made by email to: [[contact]](mailto:[contact]). The Investigator must provide the minimal information: i.e., protocol number, subject's initials and date of birth, subject number or medication code number, nature of the SAE and Investigator's attribution of causality.

All oral reports of an SAE must be confirmed within 24 hours by a written, more detailed report and signed by the Investigator. For this purpose, the Sponsor will provide the Investigator with the Serious Adverse Event Form for Clinical Trials.

All SAEs that have not resolved by the end of the study, or that have not resolved upon discontinuation of the subject's participation in the study, must be followed until either:

- the event resolves,
- the event stabilizes, or
- the event becomes non-serious

The Investigator should report any follow-up information as it becomes available.

### **9.2.3. Pregnancies**

Pregnancies occurring after the first dose of investigational product and during participation of the study are considered immediately reportable events. While not considered a SAE unless a serious criterion is met, pregnancies occurring in subjects enrolled on the study must be reported and followed to outcome. The Investigator should complete the pregnancy report eCRF within

one (1) working day of knowledge of the pregnancy. Following delivery or termination of pregnancy, the follow-up pregnancy report form should be completed on the pregnancy CRF. Spontaneous abortions should always be reported as SAEs. Follow-up information regarding the outcome of the pregnancy will be required.

### **9.3. Contacting Sponsor Regarding Safety**

Any AE considered serious by the Investigator, or that meets the SAE criteria stated in this protocol, must be reported to Drug Safety within 24 hours from the time that study site personnel first learns of the event. The study site must enter the SAE into the EDC system.

- [REDACTED]

Source documents will be requested from the study sites for SAEs and should be provided to Drug Safety. If the subject is hospitalized during the study, a copy of the hospital discharge summary should be provided to Drug Safety as soon as it becomes available. If a subject deceases during the course of the study, autopsy results should be provided to Drug Safety as soon as they become available.

## **10. SUBJECT COMPLETION**

### **10.1. Completion**

For Part A, study subject participation is complete after Day 29 (Visit 5). Subjects who withdraw their consent to be followed or are lost-to-follow-up before completion of Day 29 will not be considered to have completed the study. For Part B, study subject participation is complete after Day 57 (Visit 6). Subjects who withdraw their consent to be followed or are lost-to-follow-up before completion of Day 57 will not be considered to have completed the study.

### **10.2. Withdrawal**

All subjects have the right to withdraw from study evaluations at any time, for any reason, without prejudice; nonetheless, Investigators should attempt to encourage subjects to complete the protocol so that continued observation and follow-up measurements may be obtained.

Subjects must be withdrawn from the study for any of the following:

- Withdrawal of consent
- The subject is unwilling or unable to comply with the protocol

Other reasons for withdrawal of subjects from the study might include:

- At the discretion of the Investigator for medical reasons
- At the discretion of the Investigator or Sponsor for noncompliance
- Significant protocol deviation
- Decision by the Investigator or Sponsor

At any point, the Investigator may discontinue the subject's study participation at the discretion of the Investigator or at the request of the subject, and ensure the subject receives appropriate medical care; the Investigator may also consult the medical monitor to discuss out-of-range test results.

#### **10.2.1. Handling of Withdrawals**

Subjects will be free to withdraw from the study, including discontinuing investigational product administration, and further follow-up of the study at any time.

Should a request for early withdrawal from the study with no further follow-up be made, the subject should be encouraged to return to the study site for a last follow up visit and undergo all End-of-Study/Early-Termination assessments.

When a subject withdraws from the study prior to completing the End-of-Study Visit, the reason for withdrawal is to be documented on the eCRFs and in the source document.

#### **10.2.2. Replacements**

In order to meet the target for 50 evaluable subjects for Part B, subjects who discontinue participation in the study for non-safety related reasons will be replaced up to a maximum of 10 additional subjects.

## **11. STATISTICAL METHODS**

### **11.1. Sample Size**

The sample size for Part A (8 subjects) was selected based on clinical judgment and is not based on statistical considerations. For Part B, the assumed true standard deviation (SD) of the change from Baseline to Day 57 in the TFI overall score is 17 points. Based on the use of a one-sided two-sample t test at the  $\alpha=0.05$  level of significance, a sample size of 50 subjects (25 subjects per arm) will provide 80% power to detect a mean difference between groups of 12 points on the TFI.

### **11.2. Analysis Sets**

The intent-to-treat analysis set includes all subjects from Part A and all subjects that are randomized in Part B. All efficacy analyses will be carried out in the intent-to-treat analysis set. Subjects will be included in the group to which they were randomized.

The safety analysis set includes all subjects who receive study treatment. The safety analysis set will be used for all summaries of safety. In safety analyses and summaries, subjects will be included in the treatment group based on the treatment that was received.

### **11.3. Subject Demographics, Baseline Disease Status, and Disposition**

Descriptive statistics for subject demographics, baseline disease status, and subject disposition will be provided.

## **11.4. Study Endpoints**

### **11.4.1. Safety Endpoints – Part A**

The safety endpoints for Part A are:

- Assessment of treatment-emergent adverse events (TEAEs).
- Clinically significant adverse change from Baseline in audiometry assessments, tympanometry, and otoscopic examinations.
- Clinically significant adverse change from Baseline in clinical laboratory measurements (hematology, serum chemistry, and urinalysis) and vital signs measurements (systolic and diastolic blood pressure, pulse rate).
- Assessment of suicidality via the C-SSRS.

### **11.4.2. Plasma PK Endpoint – Part A**

The PK endpoint for Part A is:

- Plasma concentrations of gacyclidine (including (+) and (-) enantiomers of gacyclidine and possibly its metabolites).

### **11.4.3. Exploratory Efficacy Endpoints – Part A**

Exploratory efficacy endpoints for Part A are:

- Change in TFI overall score from Baseline at Day 8, 15, and 29.
- PGIC scores at Day 8, 15, and 29.

### **11.4.4. Safety Endpoints – Part B**

The safety endpoints for Part B are:

- Type and incidence of treatment-emergent adverse events (TEAEs).
- Clinically significant adverse change from Baseline in audiometry assessments, tympanometry, and otoscopic examinations.
- Clinically significant adverse change from Baseline in clinical laboratory measurements (hematology, serum chemistry, and urinalysis) and vital signs measurements (systolic and diastolic blood pressure, pulse rate).
- Assessment of suicidality via the C-SSRS.

### **11.4.5. Plasma PK Endpoint – Part B**

The PK endpoint for Part B is:

- Plasma concentrations of gacyclidine (including (+) and (-) enantiomers of gacyclidine and possibly its metabolites).

### **11.4.6. Efficacy Endpoints**

The primary efficacy endpoint for Part B is:

- Change in TFI overall score from Baseline at Day 57.

#### **11.4.7. Exploratory Efficacy Endpoints**

The exploratory efficacy endpoints for Part B are:

- Change from Baseline in the 7-day average NRS ratings of tinnitus annoyance at Weeks 2, 4, and 8.
- Change from Baseline in the 7-day average NRS ratings of tinnitus loudness at Weeks 2, 4, and 8.
- Change from Baseline in TFI overall score from Baseline at Days 15 and 29.
- The occurrence of at least a 13-point reduction in the overall TFI score from Baseline at Days 15, 29, and 57.
- Change in TFI subscale (Intrusiveness, Sense of Control, Cognitive, Sleep, Auditory, Relaxation, Quality of Life, Emotional) scores from Baseline at Days 15, 29, and 57.
- PGIC scores at Days 8, 15, 29, and 57.

#### **11.4.8. Analytic Methods for Efficacy**

For Part B, the key primary endpoint (change from Baseline to Day 57 in the TFI overall score) and all exploratory endpoints that are defined in terms of the change from baseline will be analyzed using analysis of covariance (ANCOVA) models with treatment group as a factor and the baseline value of the corresponding endpoint as a covariate. All proportion endpoints will be analyzed using Pearson's chi-square test, provided that the minimum expected cell count is at least 5. Otherwise, Fisher's exact test will be used. Correlations between endpoints will be assessed using the Pearson and Spearman correlation coefficients. All statistical analyses will be conducted using one-sided tests at the  $\alpha=0.05$  level of significance, with no adjustments for multiplicity.

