### **2.2.3. Exploratory Objectives**

- To evaluate the exploratory efficacy of OTO-313 on tinnitus annoyance using subject-reported Numeric Rating Scales (NRS).
- To evaluate the exploratory efficacy of OTO-313 on tinnitus loudness using subject-reported NRS.
- To determine the exploratory efficacy of OTO-313 on the Patient Global Impression of Change (PGIC) with respect to tinnitus severity.

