#### **8.5.4. Patient Global Impression of Change (PGIC)**

The PGIC is a patient-reported outcome that evaluates the change in overall “global” tinnitus status as perceived by the subject (Adamchic et al. 2012; van de Heyning et al. 2014). The subject is asked: “Since the beginning of the clinical study, how would you rate your tinnitus?”. The beginning of the clinical study in this context is the time prior to investigational product administration. The 7 response categories (and point scores) for the PGIC are:

- Very much improved = 3
- Much improved = 2
- Minimally improved = 1
- Unchanged = 0
- Minimally worse = -1
- Much worse = -2
- Very much worse = -3

In Part A, subjects will complete the PGIC at Days 8, 15, and 29.

In Part B, subjects will complete the PGIC at Days 8, 15, 29, and 57.

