### **11.6. Handling of Missing Data, Subject Withdrawals, and Treatment Failures**

The SAP will include details regarding the handling of missing data as well as the instructions for scoring the TFI, including handling of missing TFI questionnaire items. Every reasonable effort will be made to encourage compliance with study measurement methods and study procedures to minimize missing data.

Every reasonable effort will be made to follow subjects who withdraw from the study for safety evaluation until the date they would have completed participation.

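### Does the plan need changing because section 11.4.8 names no between-group test for the exploratory PGIC scores?

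*Combined protocol and SAP*

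**What the plan says.** Section 2.2.3 lists three exploratory objectives for Part B: annoyance NRS, loudness NRS, and "To determine the exploratory efficacy of OTO-313 on the Patient Global Impression of Change (PGIC) with respect to tinnitus severity". Section 11.4.7 gives the matching endpoint as "PGIC scores at Days 8, 15, 29, and 57". Section 8.5.4 introduces the scale with "The 7 response categories (and point scores) for the PGIC are" and assigns values from +3 (best) to -3 (worst). On timing it says "In Part B, subjects will complete the PGIC at Days 8, 15, 29, and 57", and Table 2 shows no PGIC at Screening or Baseline.

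Section 11.4.8 has two rules for comparing groups, and the synopsis repeats both. The first is that "all exploratory endpoints that are defined in terms of the change from baseline will be analyzed using analysis of covariance (ANCOVA) models", with treatment as a factor and "the baseline value of the corresponding endpoint as a covariate". For the rest, "All proportion endpoints will be analyzed using Pearson's chi-square test", with Fisher's exact test when the smallest expected count is below 5. All tests are one-sided at 0.05, with no multiplicity adjustment.

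Section 11.6 leaves further detail to a later document: "The SAP will include details regarding the handling of missing data as well as the instructions for scoring the TFI". Section 11.5.1 also refers forward to the SAP. No separate SAP text is among the documents.

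**The concern.** PGIC is the only measure serving one of the three exploratory objectives, yet neither rule can be applied to it as written. The ANCOVA needs a baseline PGIC, and none is collected. The proportion rule needs a cut, and none is given, although section 11.4.7 does state one for the TFI (a 13-point reduction).

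Four analyses could then be defended: a rank test, a comparison of mean scores, the proportion scoring at least 1, and the proportion scoring at least 2. No main visit is named among the four. If the choice were made after unblinding, the most favourable result could be presented as PGIC support for the TFI finding. With 25 subjects per arm, the four analyses can differ sharply on the same data.

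**Working it through.** **Inputs from the documents.** Section 11.1: 25 per arm, one-sided alpha 0.05, TFI difference 12, SD 17, stated power 80%. Section 8.5.4: seven ordered categories.

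**Assumptions.** The documents give no PGIC distribution. The working uses five invented placebo distributions and a latent-normal shift of 12/17 = 0.706, borrowed from the TFI.

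**Step 1: the plan's own figure.** Power = Φ(δ/(σ√(2/n)) − 1.645). Here σ√(2/n) = 17 × √(2/25) = 4.808, and 12/4.808 = 2.496. Then 2.496 − 1.645 = 0.851 and Φ(0.851) = 80.3%. The exact noncentral t gives 79.3%. The stated 80% is reproduced.

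**Step 2: power of the candidate PGIC analyses.** The mean-score t test and the tie-corrected Wilcoxon test were simulated (20,000 trials per row). The two cuts were enumerated exactly under the chi-square/Fisher rule, one-sided. Placebo percentages run from score -3 to +3.

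| Placebo distribution (%) | Improved | Mean score | Wilcoxon | Score ≥1 | Score ≥2 |
|---|---|---|---|---|---|
| 1, 4, 15, 60, 15, 4, 1 | 20% | 73% | 72% | 60% | 24% |
| 1, 5, 15, 50, 20, 7, 2 | 29% | 75% | 74% | 65% | 41% |
| 2, 4, 10, 44, 25, 10, 5 | 40% | 76% | 75% | 66% | 54% |
| 2, 5, 8, 35, 30, 15, 5 | 50% | 76% | 75% | 63% | 60% |
| 1, 3, 6, 25, 30, 25, 10 | 65% | 76% | 75% | 52% | 66% |

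The two score-based columns differ by about 1 point in every row. The weaker cut falls 16 to 49 points below Wilcoxon, so nearly all of the spread comes from the cuts.

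**Step 3: how often the two score-based tests disagree.** In a further simulation on the same five distributions (10,000 trials per setting), the mean-score and Wilcoxon tests reached different conclusions in 5-7% of trials at a shift of 0.706. With no effect, at least one of the two was significant in about 6% of trials, against a nominal 5%.

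**Step 4: two constructed data sets.** Counts run from +3 to -3.

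- *A.* OTO-313 1, 3, 10, 9, 2, 0, 0; placebo 0, 2, 6, 12, 4, 1, 0. Wilcoxon p = .034, score ≥1 p = .044, score ≥2 p = .33. Means are 17/25 = 0.68 and 4/25 = 0.16, variances 0.893 and 0.890. SE = √((0.893 + 0.890)/25) = 0.267, t = 0.52/0.267 = 1.95 on 48 df, one-sided p = .029.
- *B.* OTO-313 2, 7, 5, 7, 3, 1, 0; placebo 0, 3, 10, 8, 3, 1, 0. Wilcoxon p = .16, score ≥1 p = .39, score ≥2 p = .023. Means are 20/25 = 0.80 and 11/25 = 0.44, variances 1.750 and 1.007. SE = √((1.750 + 1.007)/25) = 0.332, t = 0.36/0.332 = 1.08, one-sided p = .14.

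In both, the rank and mean-score tests agree. The dissenting result is a cut.

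**Step 5: false positives.** Under no effect, at least one of the four analyses is significant at Day 57 in 8-10% of trials. Over all four visits, with 16 tests, this is 19-30% (between-visit correlation 0.8 to 0.4). A single fixed test repeated at four visits already gives about 11-15% over the same correlations (here of the test statistics). Much of the 19-30% therefore comes from repeated visits without adjustment, which section 11.4.8 accepts openly for every exploratory endpoint.

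**The case for a change.** The strongest case for acting is that section 11.4.8 covers all analyses with one-sided 0.05 tests, so a PGIC p-value is to be expected while its test, cut and main visit are all open. The wording of the PGIC question does ask about change, but that does not rescue the ANCOVA, since there is still no baseline value to enter. The text in section 11.6 does not mention PGIC. Naming one test before unblinding would cost a sentence.

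The textual part of this stands: the protocol does not name the test. Three parts carry less weight than they seem to.

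- Section 11.6 concerns missing data, so its silence on PGIC is no evidence that the SAP will omit it.
- The lack of a main visit is not peculiar to PGIC. The two NRS endpoints also name no main week among 2, 4 and 8.
- A cut is possible, but section 11.4.7 states its responder endpoint explicitly where it wants one, and for PGIC it lists scores.

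One caution remains. Under some hand-set treated distributions, rather than a latent shift, the mean-score and rank tests differed by up to 9 points of power, and the spread across all four analyses was 9-56 points. Near-equality of the two score tests is therefore a good approximation, not a guarantee.

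**Conclusion.** The omission is real but is missing detail, not an error. No stated rule gives a wrong PGIC result. The endpoint's own wording points to a mean-score or rank comparison. Under the assumed latent shift of 0.71 SD these have about 72-76% power at 25 per arm, about 1 point apart, and either is a sensible way to fill the gap. A Wilcoxon test would replace no worse method that the plan specifies.

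The large differences in power depend on responder cuts that the plan does not propose. Their size rests on invented PGIC distributions and an effect borrowed from another instrument. The choice would matter mainly if a cut were picked after unblinding, and nothing in the documents shows that this is intended. Naming the PGIC test in the SAP is routine analyst's work. PGIC is exploratory in a study whose primary objective is safety, and the Day 57 TFI analysis and its 80% power are unaffected. No change to the plan follows.

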
 
• Change from Baseline in the 7-day average NRS ratings of tinnitus annoyance at Weeks 2, 4, and 8.
 
• Change from Baseline in the 7-day average NRS ratings of tinnitus loudness at Weeks 2, 4, and 8.
 
• Change from Baseline in TFI overall score from Baseline at Days 15 and 29.
 
• The occurrence of at least a 13-point reduction in the overall TFI score from Baseline at Days 15, 29, and 57.
 
• Change in TFI subscale (Intrusiveness, Sense of Control, Cognitive, Sleep, Auditory, Relaxation, Quality of Life, Emotional) scores from Baseline at Days 15, 29, and 57.
 
• PGIC scores at Day 8, 15, 29, and 57.
 
	
Statistical Methods:	
Sample Size Justification:	

The sample size for Part A (8 subjects) was selected based on clinical judgment and is not based on statistical considerations. For Part B, the assumed true standard deviation (SD) of the change from Baseline to Day 57 in the TFI overall score is 17 points. Based on the use of a one-sided two-sample t test at the <math>\alpha=0.05</math> level of significance, a sample size of 50 subjects (25 subjects per arm) will provide 80% power to detect a mean difference between groups of 12 points.
	
Part A analyses:	

Safety and PK data will be summarized descriptively. The analyses of the PK data will be conducted by an independent vendor with experience in PK analyses.
	
Part B analyses:	

For Part B, the key secondary endpoint (change from Baseline to Day 57 in the TFI overall score) and all exploratory endpoints that are defined in terms of the change from baseline will be analyzed using analysis of covariance (ANCOVA) models with treatment group as a factor and the baseline value of the corresponding endpoint as a covariate. All proportion endpoints will be analyzed using Pearson's chi-square test, provided that the minimum expected cell count is at least 5. Otherwise, Fisher's exact test will be used. Correlations between endpoints will be assessed using the Pearson and Spearman correlation coefficients. All statistical analyses will be conducted using one-sided tests at the <math>\alpha=0.05</math> level of significance, with no adjustments for multiplicity.
	

Safety and PK data will be summarized descriptively.
	

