**Table 2: Time and Events Schedule Part B**

Procedure	Screening	Lead-In	Baseline  / IP Administration	Follow Up			
	Visit 1		Visit 2	Visit 3	Visit 4	Visit 5	Visit 6 /ET 
	Up to 14 days prior to start of Lead-In	Day -14 to Day -1 (+ 3 days)	Day 1	Day 8 (±2 days)	Day 15 (±2 days)	Day 29 (±2 days)	Day 57 (+3 days)
Informed consent (including privacy language/documents)	X						
Eligibility criteria	X		X				
Medical history 	X		X				
Concomitant medications	X		X	X	X	X	X
Vital sign measurements 	X		X	X	X	X	X
Height and weight measurements	X						X 
Pregnancy test 	X		X				X
Clinical laboratory tests 	X		X	X			X
Subject video 	X						
Tympanometry	X		X	X	X	X	X
Audiometry	X		X	X	X	X	X
Otoscopy	X		X	X	X	X	X
Daily NRS tinnitus electronic diary and compliance review 	X	X	X	X	X	X	X
TFI	X		X		X	X	X
PGIC				X	X	X	X
C-SSRS assessment 	X		X	X	X	X	X
Randomization 			X				
Administer investigational product 			X				
Adverse event monitoring			X	X	X	X	X
Plasma PK sampling 			X	X			

-  Baseline assessments on Day 1 are to be performed before administration of investigational product. Results from the concomitant medications review, urine pregnancy test (for females of childbearing potential), and C-SSRS (“Since Last Visit” version) must be available and reviewed by the Investigator to confirm the subject’s eligibility before randomization.
-  End-of-study procedures will be performed at Visit 6 (Day 57 ± 2 days) or upon early termination (ET) from the study.
-  Medical history to include information on demographics. Medical history also includes completion of the modified Tinnitus Sample Case History Questionnaire (TSCHQ) to capture tinnitus and related medical history information. Only changes in medical history since the Screening visit will be recorded at the Baseline (Day 1) visit.
-  Vital signs measurements include systolic and diastolic blood pressure and pulse rate.
-  Only weight is to be measured at Day 57.

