#### **Part B only**

2. Subject has subjective unilateral tinnitus and is consistently aware of their tinnitus throughout much of the waking day.
3. Subject’s self-reported duration of tinnitus is between 1 month and 6 months (30 to 180 days) prior to signing informed consent.

4. Subject has an overall score of  $\geq 25$  on the TFI at Screening and Baseline (Day 1) visits.
5. Subject is able to use the electronic diary to complete their daily tinnitus ratings and has completed at least 4 of the last 7 days of diary entries during the 2-week Lead-in period.

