#### **8.5.1.     **Tinnitus Functional Index (TFI)****

The TFI is a validated, 25-item questionnaire that can be used to scale overall severity of tinnitus and to assess treatment-related change in tinnitus (Meikle et al., 2012; Henry et al., 2015). The 25 items of the TFI represent 8 subscales covering multiple domains of tinnitus severity: 1) Intrusive, 2) Sense of Control, 3) Cognitive, 4) Sleep, 5) Auditory, 6) Relaxation, 7) Quality of Life, and 8) Emotional. Subjects answer each TFI question by rating their experience over the past week.

Completing the TFI provides an index score from 0 to 100, with higher scores representing a greater problem with tinnitus. A reduction in the TFI index score of 13 points or more is considered clinically meaningful improvement in tinnitus (Meikle et al., 2012).

In Part A, subjects will complete the TFI at Screening, Day 1 (pre-dose), and Days 8, 15, and 29.

In Part B, subjects will complete the TFI at Screening, Day 1 (pre-dose), and Days 15, 29, and 57.

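### Should the Part B TFI analysis also adjust for the Screening TFI score?

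*Combined protocol and SAP*

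**What the plan says.** Section 11.4.8 (and the Synopsis, Part B analyses) specifies, for the Day 57 TFI endpoint and every other change-from-baseline endpoint, "analysis of covariance (ANCOVA) models with treatment group as a factor and the baseline value of the corresponding endpoint as a covariate". Baseline is Day 1.

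A second pre-dose score exists. Section 8.5.1 states: "In Part B, subjects will complete the TFI at Screening, Day 1 (pre-dose), and Days 15, 29, and 57". Inclusion criterion 4 (Section 4.2) requires an overall score of at least 25 "on the TFI at Screening and Baseline (Day 1) visits". Table 2 places Screening "Up to 14 days prior to start of Lead-In", and the Lead-In lasts 14 days with a 3-day allowance. On that reading Screening falls 14 to 31 days before Day 1 (14 + 14 + 3 = 31). The heading of Section 8.2.1 instead counts the 14 days back from Baseline, so the longer gaps rest on Table 2.

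Section 11.1 sizes Part B without any covariate: "Based on the use of a one-sided two-sample t test", with "the assumed true standard deviation (SD) of the change from Baseline to Day 57 in the TFI overall score is 17 points", and "a sample size of 50 subjects (25 subjects per arm) will provide 80% power to detect a mean difference between groups of 12 points". The Synopsis calls the endpoint the "key secondary endpoint (change from Baseline to Day 57 in the TFI overall score"), and Section 2.2.2 makes TFI efficacy a secondary, preliminary objective. Section 11.6 leaves missing data and TFI scoring to a separate SAP that is not part of the document.

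**The concern.** Two scores on the same instrument are on file before randomisation, and the model uses one. The TFI asks about the past week, so a single Day 1 score carries that week's fluctuation and questionnaire noise. A second score from a different week may say more about the subject's underlying level. Because it precedes randomisation, adding it by pre-specification cannot bias the comparison, and it needs no new data. Part B has only 25 subjects per arm, and Day 57 TFI change is the only comparison it was sized for. If the Screening score carried much extra information, the plan would be accepting a wider interval than necessary.

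**Working it through.** **1. The plan's own figure.** Difference 12, SD 17, 25 per arm, one-sided 0.05. The standard error is 17 × √(2/25) = 4.81 and the noncentrality 12/4.81 = 2.50. The exact t test on 48 df gives 79.3% power, the normal approximation 80.3%. The stated 80% is reproduced, with no credit taken for any covariate.

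**2. What the planned Day 1 adjustment already gives.** Only the SD of change is stated. Assume equal TFI SDs at Day 1 and Day 57 of 18, 20 or 24, and read 17 as the SD of raw change. Then ρ(Day 1, Day 57) = 1 − 289/(2·SD²), the residual SD is SD·√(1 − ρ²), and the variance is multiplied by 47/46 for one covariate at N = 50.

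| Visit SD (assumed) | ρ | Residual SD | Power for 12 points |
|---|---|---|---|
| 18 | 0.554 | 15.0 | 86.8% |
| 20 | 0.639 | 15.4 | 85.2% |
| 24 | 0.749 | 15.9 | 83.1% |

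With Day 1 in the model, analysing change or the Day 57 score gives the same treatment effect and standard error.

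**3. What Screening can add.** Its contribution is the squared partial correlation with Day 57 given Day 1:

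pr² = (r_S57 − r_S1·r_1,57)² / [(1 − r_S1²)(1 − r_1,57²)].

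This is zero when r_S57 = r_S1·r_1,57, that is, when Screening relates to Day 57 only through Day 1. The second covariate multiplies the expected variance by 46/45. Writing R = 1 − pr² for the residual variance ratio, the net gain in subjects is 50 × (45/(46·R) − 1). If Screening adds nothing, R = 1 and the result is 50 × (45/46 − 1) = −1.1. To break even, R must fall below 45/46 = 0.978, so pr² must exceed 1/46 = 0.022.

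Example at visit SD 20, mean 50, r_S1 = 0.80, with the entry rule of 25 or more simulated at both visits. For r_S57 lower than r_1,57 by 0, 0.05 and 0.10, R = 0.932, 0.975 and 0.997, and the net gain is +2.5, +0.2 and −0.9 subjects. A difference of 0.10 in one undocumented correlation changes the sign.

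**4. The assumed scenarios, entry rule simulated.** Net gains are in subjects out of 50. Ranges cover all assumptions used; counts and medians are at mean 50.

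| Scenario | Net gain | Settings with a net loss |
|---|---|---|
| All three correlations equal, means 45–55 | +4.4 to +8.4 | none |
| r_S1 0.80 or 0.85; r_S57 0, 0.05 or 0.10 below r_1,57 | −1.1 to +6.0 | 9 of 18; median about −0.1 |
| True score decaying over time plus questionnaire noise; reliability 0.80–0.95; gap 2 or 4.4 weeks | −1.0 to +5.1 | 14 of 24; median about −0.2 |

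The mean net gain in the second and third rows is about +0.5 subjects. In the third row the losses number 7 of 8 settings at SD 18, 5 of 8 at SD 20 and 2 of 8 at SD 24. Net gains above about 3 subjects in these two rows occur only at SD 24, and there only with no fall-off from Day 1 to Screening or with reliability 0.80.

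**5. In power.** Without the entry rule, which flatters the gain, adding Screening changes power for 12 points by −0.8 to +5.4 percentage points over all settings. If 17 is instead read as the residual SD after Day 1 adjustment, power with Day 1 alone is 78.5%. With Screening added it is 77.7%, 81.4% or 85.2% for pr² of 0, 0.10 or 0.20.

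**The case for a change.** The best case for adding Screening is that the stakes are lopsided. At worst about one subject's worth of precision is lost, at best about eight are gained, for one sentence of text and no extra visit. The choice must be fixed before unblinding, because a covariate added later invites the charge of model selection. Nor is the eight a ceiling: other correlation sets give more. With r_S1 = 0.6 and both other correlations 0.7, for example, pr² corresponds to 12.0 of 50 subjects saved before the charge.

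The facts in this stand. The score exists, it is safe to use, the cost is small, and a statistician who pre-specified it could not be faulted. What does not follow is that the plan is worse without it. Comparing the two extremes is not an expected gain, and where the scenarios let correlation weaken with time or distance, the typical result is about zero. The large gains mostly need TFI scores two to four weeks apart to correlate no better than scores eight to twelve weeks apart. Nothing in the documents supports that, and Part B enrols tinnitus of 30 to 180 days' duration, where a stable score cannot be taken for granted. The change would also break the single rule of Section 11.4.8: the overall TFI would get its own model, while the NRS diary endpoints, which begin in the Lead-In, have no Screening value to use.

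**Conclusion.** The concern does not hold. Baseline-adjusted ANCOVA on the Day 1 score is a standard, valid analysis, it takes most of the precision available from pre-dose TFI, and the sample size does not depend even on that. Adding the Screening score would change precision by roughly −1 to +8 subjects out of 50 over the scenarios examined, and centres near zero once correlations are allowed to fall off. Those figures rest on assumed visit SDs (18–24), means (45–55), reliabilities and correlations; only the SD of change, 17, comes from the document, and the range is not a strict bound. The covariates in the separate SAP could not be checked. With a gain of unknown sign, on an endpoint whose Part B objective is secondary and preliminary, leaving the Screening score to its eligibility role is a reasonable choice and calls for no change.
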